#### *Acute First-Day Response*

- *Determine the change in PAPm between baseline and first 3 hours after the first dose of Entresto*
  - *Statistical Plan: These changes in PAPm from baseline to 2 hours after Entresto constitute a distribution of continuous data. The distribution of change in PAPm from the morning baseline visit (before Entresto) to 2 hours after the first dose of Entresto will be assessed in both groups. The distribution of changes will be assessed for normality. If the distributions are normal, the results will be presented as means with standard errors. If the distributions are not normal, the results will be presented as medians with interquartile ranges.*

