##### Acute First-Day Response

- Determine the change in PAPm between baseline and first 3 hours after the first dose of Entresto

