### *Schedule of Administration*

Entresto is administered twice a day. On day 5 and day 47, patients will be instructed to hold their other morning medications and take only their first dose of Entresto and placebo or ACEi/ARB and placebo. They will then be asked to measure their PA pressures using their home CardioMEMS device 1, 2, and 3 hours after their first dose of Entresto or ACEi/ARB.

Both groups will do this on day 5 and day 47. On day 5, Group A will be measuring the first dose effect of Entresto and Group B will be measuring the first dose effect of ACEi/ARB after the washout period. On day 47, Group A will be measuring the acute effects of Entresto after 6 weeks of therapy and Group B will be measuring the first dose effects of Entresto.

Patients will also be asked to complete this “acute PA pressure measurement” schedule, i.e. holding morning medications, measuring PA pressure before and at hours 1, 2, 3 after their morning dose of Entresto or ACEi/ARB, after any dosing change.

On all other days, patients will take their morning dose of Entresto or ACEi/ARNB and placebo with their other morning medications. The evening dose of Entresto or ACEi/ARB and placebo can be taken with other evening medications as well.

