**PA pressure measurements done by the patient at home**

“Acute PAP Measurement” (Done on Days 5 and 47 and done on the first day of any dosing change )

- Baseline Time 1 (time before taking medication) – 1st PA pressure measurement
- Time of measurement 1 (1 hour post dose) – 2nd PA pressure measurement
- Time of measurement 2 (2 hours post dose) – 3rd PA pressure measurement
- Time of measurement 3 (3 hours post dose) – 4th PA pressure measurement
- Heart rate
- PA pressures
- Any instructions required to optimize tracing (e.g. breath-hold, turn on pillow, reposition wand)
- Any comments on PA tracing morphology

Routine Daily Pulmonary Pressure Data

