#### Acute First-Day Response

- Change in PAPm between baseline and first 3 hours after the first dose of Entresto

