### Secondary Endpoints:

- *Determine the mean change in PAPm in both groups on Entresto from week 12 to week 32 in longitudinal study*
  - *Statistical Plan: The changes in PAPm from week 12 to week 32 constitute continuous data. The distribution of average change in PAPm from week 8 to week 32 will be assessed in both group A and B. The distribution of changes in*

PAPm will be assessed for normality. If the distributions are normal, the results will be presented as means with standard errors. If the distributions are not normal, the results will be presented as medians with interquartile ranges.

- *Determine the difference between mean change in PAPm from baseline on ACEI/ARB to 6 weeks on Entresto (Groups A and B)*
  - Statistical Plan: The distribution of the average change in PAPm from baseline to 6 weeks will be assessed in Group A and combined with the distribution of change in PAPm from week 6 to week 12 in Group B. The combined distributions will be assessed for normality. If the combined distribution of changes in PAPm is normal, the results will be presented as means with standard errors. If the distributions are not normal, the results will be presented as medians with interquartile ranges.
  
- *Determine the impact of therapy over time on standard 6 minute walk test, assessing distance walked and changes in PAPm during recovery after the walk.*
  - Statistical Plan: These changes in distance walked from baseline to 6 weeks constitute continuous data. Therefore, the distribution of average changes in PAPm from baseline to 6 weeks will be assessed in Group A and Group B. If both distributions are normal, t-testing will be performed to compare the mean changes between groups. If the distributions are not normal, Wilcoxon testing will be used.  $P < 0.05$  will be significant.

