### **b. Drug Side Effects and Toxicities**

Subjects are not exposed to any risks other than those occurring during standard approved care for HFrEF, which includes both the medication Entresto and the CardioMEMS monitoring device. The only way in which their enrollment in the study differs from standard of care is that they will undergo more frequent monitoring, which increases the safety of drug titration to avoid lowering of filling pressures to levels that might be associated with postural hypotension when Entresto is added to their previous HF regimen.

It is unlikely that there will be any adverse effects of holding ACEI/ARB for 2 days (minimum 36 hours as per FDA labelling) at the beginning of the study. For the A group, this would occur anyway for safety, as a washout period of at least 2 days (minimum 36 hours as per FDA labelling) is required before initiation of Entresto. For the B group who will resume ACEI/ARB after 2 days (minimum 36 hours as per FDA labelling), such pauses in one component of therapy

are common around the time of surgery and are not anticipated to lead to any symptoms, as the other medications will be continued as usual.

*Common:* Based on Novartis' published prescribing guidelines for Entresto and previous clinical trials, the major side effects are similar to ACEi/ARB therapy: hypotension, hyperkalemia and renal dysfunction. All of these potential side effects will all be monitored for by study staff with frequent lab work, as is standard of care. In addition, due to their enrollment in this trial, hemodynamic assessment (including blood pressure) will be checked at each visit and PA pressures will be monitored daily by patient and reviewed by the study staff. This will increase the patient's level of safety as compared to standard clinical practice. Any dose changes will be followed by "acute PAP measurements" the next day and safety lab work as clinically indicated.

*Uncommon:* Similar to ACEi therapy, Entresto has a small risk of angioedema (0.2% in the Entresto group compared to 0.1% in the Enalapril group in the PARADIGM trial). These events have to date not been known to cause airway compromise.

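### The acute first-dose co-primary is defined over 3 hours but analysed at 2 hours only, as an uncontrolled pre/post change, while the concurrent comparison readings enter no analysis

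*Combined protocol and SAP*

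**What the plan says.** The Study Endpoints list gives the acute co-primary as "Change in PAPm between baseline and first 3 hours after the first dose of Entresto". Section II.a (co-primary objectives) and the objective line that opens the Acute First-Day Response entry under Statistical Analysis use the same 3-hour window.

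The plan beneath that objective line refers to 2 hours twice. It says that the PAPm change "from the morning baseline visit (before Entresto) to 2 hours after the first dose of Entresto will be assessed in both groups". The result is to be shown as a mean with standard error, or as a median with interquartile range. No test is named.

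The readings are described in V.b (Schedule of Administration), V.c (Devices to be Used), V.e (Data to be Collected) and the home collection sheet. On days 5 and 47 patients measure at home before the dose and at 1, 2 and 3 hours after it. They are told to "hold their other morning medications and take only their first dose of Entresto and placebo or ACEi/ARB and placebo". On day 5 Group A takes its first Entresto dose, while "Group B will be measuring the first dose effect of ACEi/ARB after the washout period". On day 47 Group B takes its first Entresto dose and Group A measures its response after 6 weeks of Entresto. VII.b (Drug Side Effects and Toxicities) confirms that both groups pause ACEi/ARB at the start: "For the B group who will resume ACEI/ARB after 2 days".

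**The concern.** The endpoint and its analysis describe different quantities. A co-primary announced as a 3-hour response would be reported from a single reading per patient at 2 hours. The 1-hour and 3-hour values would be left without any planned use. If this is not settled beforehand, the time point reported could be chosen after the data are seen.

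The planned result also has no comparator. A change between a pre-dose morning reading and one taken 2 hours later mixes any effect of the dose with time of day and with repeated measurement. The documents give neither the size nor the direction of such changes, so they could mimic an effect or hide one. Readings that would allow a comparison between randomised groups are already being collected, but no analysis uses them.

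**Working it through.** **Definition against analysis**

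| Place | Window or time point |
|---|---|
| II.a objectives | first 3 hours |
| Study Endpoints | first 3 hours |
| Statistical Analysis, objective line | first 3 hours |
| Statistical Analysis, plan text (twice) | 2 hours |
| V.b, V.c, V.e and home collection sheet | pre-dose, then 1, 2 and 3 hours |

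The plan text names the baseline as a morning visit. The data sections define it as the home reading taken before the dose on the same morning. This is a difference of wording, but it should be corrected.

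**Readings in and out of the analysis** (10 patients per group, from Power Analysis)

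- Post-dose readings at the first Entresto dose (Group A day 5, Group B day 47): 20 × 3 = 60. Used at 2 hours: 20. Not used: 60 − 20 = 40.
- Group B on day 5: 10 × 3 = 30 post-dose and 10 pre-dose readings, none in any analysis.
- Group A on day 47: 10 × 3 = 30 post-dose and 10 pre-dose readings, none in any analysis.

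None of the entries from Co-Primary Endpoints to Tertiary Endpoints under Statistical Analysis uses these last two sets.

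**Inputs for precision**

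Power Analysis gives no effect size, SD or power for the acute endpoint, so there is no stated figure to reproduce. It reports an SD of 3–4 mm Hg for pressures over 5-day periods, which is not the SD of an acute change. I take 3–4 mm Hg as an assumed range for the change SD. The 6.8 in the same section is a tolerance. For a 5 mm Hg change with n = 20, 90% power and two-sided 0.05, the normal approximation allows an SD up to 5 × √20 / (1.960 + 1.282) = 6.90. It is therefore shown below only as a stress case.

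**Supportive contrast on day 5, Group A versus Group B (10 v 10)**

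Adjusting for the pre-dose value leaves 20 − 3 = 17 degrees of freedom, t = 2.110. No gain from the covariate is assumed.

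- SE = SD × √(2/10): 1.34 at SD 3, 1.79 at SD 4.
- 95% CI half-width = 2.110 × SE: 2.83 at SD 3, 3.77 at SD 4 (6.42 at SD 6.8).
- Difference detectable with 80% power, two-sided 0.05, noncentral t: 3.99 at SD 3, 5.32 at SD 4 (9.04 at SD 6.8).

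**Pre/post change, by group and combined**

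- By group, n = 10: 2.262 × SD/√10 = 2.15 at SD 3, 2.86 at SD 4.
- Combined, n = 20: 2.093 × SD/√20 = 1.40 at SD 3, 1.87 at SD 4.
- Ratio 2.15/1.40 ≈ 1.5. This is sample-size arithmetic and does not measure the 2-hour versus 3-hour mismatch. The documents give nothing from which to estimate how much that mismatch would alter the result.

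**The case against.** Two hours lies within the first 3 hours, the analysis text is the more specific of the two, and this is a 20-patient pilot. The sponsor could fairly say that 2 hours was always meant. That is a legitimate choice, but the objectives and endpoint list must then say so. The independent reviewer named in IX.c does look at acute and first-dose pressures. That is oversight and supplies no analysis. It is also true that the day-5 contrast is imprecise and answers a narrower question than the pre/post change. It can therefore only be supportive.

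A reader might infer more than the documents support:

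- **That day 5 is the only concurrent comparison of the randomised groups.** It is not, because day 47 is a second. It is less comparable, since Group B then starts Entresto after a washout while Group A is already 6 weeks into Entresto.
- **That renewed renin-angiotensin blockade is a non-drug explanation to be removed.** Section I.a states that Entresto contains valsartan, so renewed blockade is part of its first-dose effect. Only time of day and repeated measurement are non-drug rivals.
- **That a hypothesis test is planned but left unspecified.** The 6-week co-primary names its tests and significance level, whereas the acute entry uses the wording applied elsewhere to results that are only summarised. Despite the directional hypothesis in I.c, the natural reading is descriptive.
- **That the groups are to be pooled.** For the 6-week secondary endpoint the plan says "combined with the distribution of change in PAPm from week 6 to week 12 in Group B", while the acute entry refers only to both groups. If anything, that points to separate reporting.

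**Conclusion.** The mismatch is real and should be fixed. Three places define a 3-hour endpoint and the analysis uses 2 hours, which leaves 40 of 60 post-dose readings without a planned use. As planned, the result is an uncontrolled change and cannot support a claim of a drug effect by itself. The readings for a randomised day-5 contrast exist but are in no analysis.

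The text comparison and the counts rest on the documents alone. The precision figures rest on an assumed change SD of 3–4 mm Hg. The documents do not show that the result would be wrong in either direction, or that any non-drug change is large.

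**What to change.** 1. Use one definition in the objectives, Study Endpoints and Statistical Analysis. Either take the mean of the 1-, 2- and 3-hour home PAPm minus the same-morning pre-dose home PAPm, or use 2 hours throughout. The first keeps the stated window but would dilute an effect confined to one hour. In the analysis text, replace the reference to a baseline visit with the same-morning pre-dose home reading.
2. Add a supportive Group A versus Group B contrast on day 5, adjusted for the pre-dose value, with a 95% CI. Interpret it as Entresto relative to restarting ACEi/ARB. State that no drug effect will be claimed from the pre/post change alone, and that a null contrast would not show absence of an acute effect.
3. As clarifications, say that the pre/post endpoint is descriptive, and report Group A day 5 and Group B day 47 by group as well as combined. Note beside the combined figure that Group B's day 47 follows up to 6 weeks of possible ACEi/ARB titration (V.b), which Group A's day 5 does not.

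The cost is wording in three places and one extra analysis. No patients, visits or readings are added.

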### Secondary Endpoints:

- *Determine the mean change in PAPm in both groups on Entresto from week 12 to week 32 in longitudinal study*
  - *Statistical Plan: The changes in PAPm from week 12 to week 32 constitute continuous data. The distribution of average change in PAPm from week 8 to week 32 will be assessed in both group A and B. The distribution of changes in*

PAPm will be assessed for normality. If the distributions are normal, the results will be presented as means with standard errors. If the distributions are not normal, the results will be presented as medians with interquartile ranges.

- *Determine the difference between mean change in PAPm from baseline on ACEI/ARB to 6 weeks on Entresto (Groups A and B)*
  - Statistical Plan: The distribution of the average change in PAPm from baseline to 6 weeks will be assessed in Group A and combined with the distribution of change in PAPm from week 6 to week 12 in Group B. The combined distributions will be assessed for normality. If the combined distribution of changes in PAPm is normal, the results will be presented as means with standard errors. If the distributions are not normal, the results will be presented as medians with interquartile ranges.
  
- *Determine the impact of therapy over time on standard 6 minute walk test, assessing distance walked and changes in PAPm during recovery after the walk.*
  - Statistical Plan: These changes in distance walked from baseline to 6 weeks constitute continuous data. Therefore, the distribution of average changes in PAPm from baseline to 6 weeks will be assessed in Group A and Group B. If both distributions are normal, t-testing will be performed to compare the mean changes between groups. If the distributions are not normal, Wilcoxon testing will be used.  $P < 0.05$  will be significant.
  - Statistical Plan (*Intensive Phase, patients in both groups as their own control after 6 weeks of Entresto- Group A: week 6 minus baseline; Group B: week 12 minus week 6*): The change in PAPm from pre to peak exercise at baseline and at 5 minute intervals for 30 minutes of recovery will be compared to the change in PAPm from pre to peak exercise and at 5 minute intervals for 30 minutes of recovery at 6 weeks in Group A. If the distributions are normal, the results will be presented as means with standard errors. If the distributions are not normal, the results will be presented as medians with interquartile ranges. The change in PAPm from pre to peak exercise at 6 weeks and at 5 minute intervals for 30 minutes of recovery will be compared to the change in PAPm from pre to peak exercise and at 5 minute intervals for 30 minutes of recovery at week 12 in Group B. If the distributions are normal, the results will be presented as means with standard errors. If the distributions are not normal, the results will be presented as medians with interquartile ranges.

- Statistical Plan (*Intensive Phase, patients on the Entresto Group A: week 6 minus baseline*) compared to patients on continued ACEi/ARB therapy; Group B: week 6 minus baseline): The change in PAPm from pre to peak exercise and at 5 minute intervals for 30 minutes of recovery at 6 weeks in Group A will be compared to the change in PAPm from pre to peak exercise and at 5 minute intervals for 30 minutes of recovery at 6 weeks in Group B. If both distributions are normal, t-testing will be performed to compare the mean changes between groups. If the distributions are not normal, Wilcoxon testing will be used.  $P < 0.05$  will be significant.
- Statistical Plan (*Longitudinal Phase, Patients in both groups - week 32 minus week 12*): The change in PAPm from pre to peak exercise and at 5 minute intervals for 30 minutes of recovery at 32 weeks will be compared to the change in PAPm from pre to peak exercise and at 5 minute intervals for 30 minutes of recovery at 12 weeks in both groups. If the distributions are normal, the results will be presented as means with standard errors. If the distributions are not normal, the results will be presented as medians with interquartile ranges.
- *Determine the impact of therapy over time on standard double Master's step test, assessing changes in PAPm during recovery after the test.*
  - Statistical Plan (*Intensive Phase, patients in both groups as their own control after 6 weeks of Entresto- Group A: week 6 minus baseline; Group B: week 12 minus week 6*): The change in PAPm from pre to peak exercise at baseline and at 5 minute intervals for 30 minutes of recovery will be compared to the change in PAPm from pre to peak exercise and at 5 minute intervals for 30 minutes of recovery at 6 weeks in Group A. If the distributions are normal, the results will be presented as means with standard errors. If the distributions are not normal, the results will be presented as medians with interquartile ranges. The change in PAPm from pre to peak exercise at 6 weeks and at 5 minute intervals for 30 minutes of recovery will be compared to the change in PAPm from pre to peak exercise and at 5 minute intervals for 30 minutes of recovery at week 12 in Group B. If the distributions are normal, the results will be presented as means with standard errors. If the distributions are not normal, the results will be presented as medians with interquartile ranges.
  - Statistical Plan (*Intensive Phase, patients on the Entresto Group A: week 6 minus baseline*) compared to patients on continued ACEi/ARB therapy; Group B: week 6 minus baseline): The change in PAPm from pre to peak exercise and at 5 minute intervals for 30 minutes of recovery at 6 weeks in Group A will be compared to the change in PAPm from pre to peak exercise and at 5 minute intervals for 30 minutes of recovery at 6 weeks in Group B. If both distributions are normal, t-testing will be performed to compare the mean changes between

groups. If the distributions are not normal, Wilcoxon testing will be used.  $P < 0.05$  will be significant.

- Statistical Plan (*Longitudinal Phase, Patients in both groups - week 32 minus week 12*): The change in PAPm from pre to peak exercise and at 5 minute intervals for 30 minutes of recovery at 32 weeks will be compared to the change in PAPm from pre to peak exercise and at 5 minute intervals for 30 minutes of recovery at 12 weeks in both groups. If the distributions are normal, the results will be presented as means with standard errors. If the distributions are not normal, the results will be presented as medians with interquartile ranges.
- *Determine the impact of therapy over time on standard Handgrip test, assessing changes in PAPm, blood pressure and heart rate during test and recovery.*
  - Statistical Plan (*Intensive Phase, patients in both groups as their own control after 6 weeks of Entresto- Group A: week 6 minus baseline; Group B: week 12 minus week 6*): The change in PAPm, blood pressure and heart rate from pre to peak isometric exercise at baseline and at 5 minute intervals for 15 minutes of recovery will be compared to the changes in PAPm, blood pressure and heart rate from pre to peak isometric exercise and at 5 minute intervals for 15 minutes of recovery at 6 weeks in Group A. If the distributions are normal, the results will be presented as means with standard errors. If the distributions are not normal, the results will be presented as medians with interquartile ranges. The change in PAPm, blood pressure and heart rate from pre to peak isometric exercise at 6 weeks and at 5 minute intervals for 15 minutes of recovery will be compared to the change in PAPm, blood pressure and heart rate from pre to peak isometric exercise and at 5 minute intervals for 15 minutes of recovery at week 12 in Group B. If the distributions are normal, the results will be presented as means with standard errors. If the distributions are not normal, the results will be presented as medians with interquartile ranges.
  - Statistical Plan (*Intensive Phase, patients on the Entresto Group A: week 6 minus baseline) compared to patients on continued ACEi/ARB therapy; Group B: week 6 minus baseline*): The change in PAPm, blood pressure and heart rate from pre to peak isometric exercise and at 5 minute intervals for 15 minutes of recovery at 6 weeks in Group A will be compared to the change in PAPm, blood pressure and heart rate from pre to peak isometric exercise and at 5 minute intervals for 15 minutes of recovery at 6 weeks in Group B. If both distributions are normal, t-testing will be performed to compare the mean changes between groups. If the distributions are not normal, Wilcoxon testing will be used.  $P < 0.05$  will be significant.
  - Statistical Plan (*Longitudinal Phase, Patients in both groups - week 32 minus week 12*): The change in PAPm, blood pressure and heart rate from pre to peak

isometric exercise and at 5 minute intervals for 15 minutes of recovery at 32 weeks will be compared to the change in PAPm, blood pressure and heart rate from pre to peak isometric exercise and at 5 minute intervals for 15 minutes of recovery at 12 weeks in both groups. If the distributions are normal, the results will be presented as means with standard errors. If the distributions are not normal, the results will be presented as medians with interquartile ranges.

- *Determine the impact of therapy over time on standard Stroop Color test, assessing changes in PAPm, blood pressure and heart rate during test and recovery.*
  - *Statistical Plan (Intensive Phase, patients in both groups as their own control after 6 weeks of Entresto- Group A: week 6 minus baseline; Group B: week 12 minus week 6):* The change in PAPm, blood pressure and heart rate during Stroop Color test at baseline and at 5 minute intervals for 15 minutes of recovery will be compared to the changes in PAPm, blood pressure and heart rate during Stroop Color test and at 5 minute intervals for 15 minutes of recovery at 6 weeks in Group A. If the distributions are normal, the results will be presented as means with standard errors. If the distributions are not normal, the results will be presented as medians with interquartile ranges. The change in PAPm, blood pressure and heart rate during Stroop Color test at 6 weeks and at 5 minute intervals for 15 minutes of recovery will be compared to the change in PAPm, blood pressure and heart rate during Stroop Color test and at 5 minute intervals for 15 minutes of recovery at week 12 in Group B. If the distributions are normal, the results will be presented as means with standard errors. If the distributions are not normal, the results will be presented as medians with interquartile ranges.
  - *Statistical Plan (Intensive Phase, patients on the Entresto Group A: week 6 minus baseline) compared to patients on continued ACEi/ARB therapy; Group B: week 6 minus baseline):* The change in PAPm, blood pressure and heart rate during Stroop Color test and at 5 minute intervals for 15 minutes of recovery at 6 weeks in Group A will be compared to the change in PAPm, blood pressure and heart rate during Stroop Color test and at 5 minute intervals for 15 minutes of recovery at 6 weeks in Group B. If both distributions are normal, t-testing will be performed to compare the mean changes between groups. If the distributions are not normal, Wilcoxon testing will be used.  $P < 0.05$  will be significant.
  - *Statistical Plan (Longitudinal Phase, Patients in both groups - week 32 minus week 12):* The change in PAPm, blood pressure and heart rate during Stroop Color test and at 5 minute intervals for 15 minutes of recovery at 32 weeks will be compared to the change in PAPm, blood pressure and heart rate during Stroop Color test and at 5 minute intervals for 15 minutes of recovery at 12 weeks in both groups. If the distributions are normal, the results will be presented as means with

standard errors. If the distributions are not normal, the results will be presented as medians with interquartile ranges.

- *Determine the change in NT-proBNP and the BNP/NT-proBNP ratio*
  - Statistical Plan (*Intensive Phase, patients in both groups as their own control - Group A: week 4 minus baseline; Group B: week 8 minus week 4*) The change in NT-proBNP from baseline to week 6 will be assessed in Group A and combined with the change in NT-proBNP levels from week 6 to week 12 in Group B. These distributions will be continuous distributions. If the distributions are normal, the results will be presented as means with standard errors. If the distributions are not normal, the results will be presented as medians with interquartile ranges.
  - Statistical (*Intensive Phase, patients on the Entresto Group A: week 6 minus baseline) compared to patients on continued ACEi/ARB therapy; Group B: week 6 minus baseline*): The change in NT-proBNP levels will be assessed from baseline to week 6 in Group A and Group B. If both distributions are normal, t-testing will be performed to compare the mean changes between groups. If the distributions are not normal, Wilcoxon testing will be used.  $P < 0.05$  will be significant.
  - Statistical Plan (*Longitudinal Phase, Patients in both groups - week 32 minus week 8*): The change in NT-proBNP levels from week 12 to week 32 will be assessed in both groups. If the distributions are normal, the results will be presented as means with standard errors. If the distributions are not normal, the results will be presented as medians with interquartile ranges.

Tertiary Endpoints (Exploratory):

- Relationship of change in PAPm to change in the questions in the Kansas City Cardiomyopathy Questionnaire (KCCQ) 3, 7,8,9 which describe the severity of symptoms of congestion
  - Statistical Plan (*Intensive Phase, patients in both groups as their own control - Group A: week 6 minus baseline; Group B: week 12 minus week 6*): The change in KCCQ questions #3, 7, 8 & 9 will be assessed from baseline to week 6 in Group A and from week 6 to week 12 in Group B. The change in “score” for these four questions will be a continuous distribution when the groups are combined. If the combined distribution is normal, the results will be presented as means with standard errors. If the distributions are not normal, the results will be presented as medians with interquartile ranges.

- Statistical Plan (*Intensive Phase, patients on the Entresto Group A: week 6 minus baseline*) compared to patients on continued ACEi/ARB therapy; Group B: week 6 minus baseline): The change in KCCQ questions #3, 7, 8 & 9 from baseline to week 4 will be assessed in Group A and Group B. The change in “score” for these four questions will be a continuous distribution for both groups. If both distributions are normal, t-testing will be performed to compare the mean changes between groups. If the distributions are not normal, Wilcoxon testing will be used.  $P < 0.05$  will be significant.
- Statistical Plan (*Longitudinal Phase, Patients in both groups - week 32 minus week 12*): The change in KCCQ questions #3, 7, 8 & 9 from week 12 to week 32 will be assessed in both groups. The change in “score” for these four questions will be a continuous distribution when the groups are combined. If the distribution is normal, the results will be presented as means with standard errors. If the distributions are not normal, the results will be presented as medians with interquartile ranges.
- Mean change in total daily diuretic dose while on Entresto
  - Statistical Plan (*Intensive Phase, patients in both groups as their own control - Group A: week 6 minus baseline; Group B: week 12 minus week 6*): The change in total daily diuretic dose from baseline to week 6 in Group A and from week 6 to week 12 in Group B will be assessed. If the distributions are normal, the results will be presented as means with standard errors. If the distributions are not normal, the results will be presented as medians with interquartile ranges.
  - Statistical Plan (*Intensive Phase, patients on the Entresto Group A: week 6 minus baseline*) compared to patients on continued ACEi/ARB therapy; Group B: week 6 minus baseline): The change in total daily diuretic dose score from baseline to week 6 in Group A and Group B will be assessed. If both distributions are normal, t-testing will be performed to compare the mean changes between groups. If the distributions are not normal, Wilcoxon testing will be used.  $P < 0.05$  will be significant.
  - Statistical Plan (*Longitudinal Phase, Patients in both groups - week 32 minus week 12*): The change in total daily diuretic dose from week 12 to week 32 will be assessed in both groups. If the distributions are normal, the results will be presented as means with standard errors. If the distributions are not normal, the results will be presented as medians with interquartile ranges.

